16.6 Analysis Plan for Secondary Outcome and Translational Endpoints

The below analyses will be done on FGF19 positive patients. The analyses will also be performed on FGF19 negative patients as exploratory analyses.

16.6.1 Objective Response

Objective response by RECIST v1.1 criteria will be estimated using objective response rate (ORR) where ORR is defined as the number of evaluable patients achieving a response (PR or CR per RECIST v1.1) during treatment with study therapy divided by the total number of evaluable patients. Point estimates will be generated for objective response rates along with 95% binomial confidence intervals²⁸.

16.6.2 Overall Survival

Overall survival time is defined as the time from registration to death due to any cause. Patients who are alive will be censored at last follow-up for overall survival. The distribution of survival time will be estimated using the method of Kaplan-Meier²⁹. OS medians will be estimated along with 95% confidence intervals.

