4.2 Survival Follow-up/Event Monitoring

NOTE: Survival Follow-up/Event Monitoring on this study will cease as of 31Aug2025.

NOTE: Timelines are approximate and not meant to represent exact dates.

	Survival Follow-up		
	q. 6 months	Death	New Primary
Survival Follow-up ¹	X	X	At each occurrence

1. If a patient is still alive 5 years after registration, no further follow-up is required.

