7.3 Return to consenting institution

For this protocol, the patient must return to the consenting institution for evaluation at least every 21 days ± 3 days during treatment for first 9 cycles. Beginning with Cycle 10 patients must return at least every 42 days ± 7 days.

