13.0 Treatment/Follow-up Decision at Evaluation of Patient

- 13.1 Continuation of treatment

Patients who are CR, PR, or SD will continue treatment per protocol.

- 13.2 Progressive disease (PD)

Patients who develop PD while receiving therapy will go to the survival follow-up phase.

- 13.3 Off protocol treatment

Patients who go off protocol treatment for reasons other than PD will go to the clinical follow-up/observation phase per Section 4.0. Participants will be required to return to the consenting site for follow-up until disease progression, new anti-cancer therapy, death, withdrawal of consent for clinical followup, or a maximum of 18 months from Registration.

- 13.4 Duration of therapy for CR

Patients who achieve a CR will receive a maximum total of 35 cycles (i.e., 2 years). After 35 cycles, they will go to survival follow-up/event monitoring. Subsequent treatment is at the discretion of their attending physician.

- 13.5 Duration of therapy for PR or SD

Patients who are in PR or SD will continue on therapy for a total of 35cycles (i.e., 2 years). After 35 cycles, they will go to survival follow-up/event monitoring. Subsequent treatment is at the discretion of their attending physician.

- 13.6 Ineligible

A patient is deemed *ineligible* if after registration, it is determined that at the time of registration, the patient did not satisfy each and every eligibility criteria for study entry. If the patient received treatment, the patient may continue treatment at the discretion of the physician as long as there are not safety concerns. The patient will continue in the Active Monitoring/Treatment phase of the study, per [Section 4.0](#) of the protocol.

- If the patient never received treatment, on-study material must be submitted. Survival follow-up/event monitoring will be required per [Section 4.0](#) of the protocol.

- 13.7 Major violation

A patient is deemed a *major violation*, if protocol requirements regarding treatment in Cycle 1 of the initial therapy are severely violated that evaluability for primary endpoint is questionable. If the patient received treatment, the patient may continue treatment at the discretion of the physician as long as there are not safety concerns. The patient will continue in the Active Monitoring/Treatment phase of the study, per [Section 4.0](#) of the protocol.

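### Overall survival censors patients at a last contact that may be up to about 6 months old, with no closing vital-status check before follow-up stops on 31 Aug 2025; if late deaths are reported promptly, Kaplan-Meier OS is biased downward near the cut

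*Combined protocol and SAP*

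**What the plan says.** Section 16.6.2 defines the endpoint: "Overall survival time is defined as the time from registration to death due to any cause". It then sets the censoring rule: "Patients who are alive will be censored at last follow-up for overall survival". The curve is estimated by Kaplan-Meier, with a median and 95% confidence interval. OS is a secondary endpoint (Sections 2.22 and 16.2).

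Contact frequency depends on the phase a patient is in:

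- **On treatment:** every 21 days through Cycle 9. After that, Section 7.3 says "Beginning with Cycle 10 patients must return at least every 42 days".
- **Off treatment without progression (PD):** Section 13.3 says "Patients who go off protocol treatment for reasons other than PD will go to the clinical follow-up/observation phase per Section 4.0". The test schedule in Section 4.1 puts those visits at 9-week intervals, to at most 18 months after registration.
- **After PD:** Section 13.2 says "Patients who develop PD while receiving therapy will go to the survival follow-up phase". Patients who complete 35 cycles (13.4, 13.5) or start new anti-cancer therapy (13.9a) also go there. Section 4.2 schedules this contact every 6 months, with death marked in its own column, and adds that "Timelines are approximate and not meant to represent exact dates".

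Two limits apply. One is individual: "If a patient is still alive 5 years after registration, no further follow-up is required". The other is a calendar date: "Survival Follow-up/Event Monitoring on this study will cease as of 31Aug2025". Neither Section 4.2 nor Section 16.6.2 asks for a vital-status check of survivors at that date, and 16.6.2 does not name it as the OS cut-off.

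**The concern.** Kaplan-Meier assumes that the time at which a patient is censored carries no information about whether that patient has died. That fails if a death can reach the database when it happens while a survivor's time stops at the last contact. Take two patients in survival follow-up, both last contacted four months before the cut. If one dies a month before the cut and the death is reported, three further months and an event are counted. If the other is alive throughout, nothing after the last contact is counted. In the months before the cut the deaths stay in and the survivors drop out, so the estimated hazard is too high.

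At stake are the OS median, its interval and the late part of the curve. A confidence interval does not correct a systematic error of this kind. The patients most exposed are those past PD, where contact is sparsest.

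**Working it through.** **The plan's own figures.** The plan states no OS figure, so there is none to reproduce. Its two progression-free survival (PFS) distributions in Section 16.5 are used in run 2. At 27 weeks, 27/52 = 0.519 years, exp(-(0.519/0.3)^0.6667) = 0.24 and exp(-(0.519/0.73)^0.885) = 0.48. These are close to the stated 25% and 47%, so the scales are in years.

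**Mechanism.** The estimator is S(t) = product of (1 - d/n) over death times. As an invented illustration, let 8 patients be at risk, with 2 dying at reported dates shortly before the cut.
- Survivors followed to the cut: 7/8 x 6/7 = 0.75.
- Three of the six survivors last contacted before the first death: 4/5 x 3/4 = 0.60.

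With 6-monthly contact, the gap between last contact and cut runs from 0 to 6 months and averages 6/2 = 3 months if contacts are evenly spread.

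**Run 1: exponential OS.** Large-sample simulation.
- From the documents: OS medians 10.7-13.6 months (Section 1.1); contact intervals from Sections 4.1, 4.2 and 7.3.
- Assumed: median 6 months on treatment; 25% off treatment without PD and on 9-weekly visits; every death known when it occurs.

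The difference is the median with survivors censored at last contact minus the median with survivors censored at the cut.

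| Accrual | Cut after last patient | Median too low by |
|---|---|---|
| 12 months | 6 months | up to about 1.6 months |
| 24-36 months | 6 months | about 0.3-0.7 months |
| 24-36 months | 12 months | at most about 0.25 months |
| any of these | 18 months or later | about 0 |

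If half of the late deaths are prompt, the +6 differences roughly halve. If none are, they are near zero.

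**Run 2: OS built from the plan's PFS distributions.** Assumed: survival after progression exponential with median 9 months (25% scenario) or 7 months (47% scenario); 15% of PFS events are deaths; 25% on 9-weekly visits; 6-monthly contacts counted from PD. The true OS medians are then about 11.7 and 14.3 months. KM median under the plan's rule, by share of late deaths reported promptly:

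| Accrual, cut | True | All | Half | None |
|---|---|---|---|---|
| 11 months, +6 | 11.7 | 10.13 | 10.92 | 12.29 |
| 11 months, +6 | 14.3 | 12.50 | 13.78 | 16.63 |
| 24 months, +6 | 11.7 | 11.08 | 11.44 | 11.91 |
| 24 months, +6 | 14.3 | 13.65 | 14.23 | 14.85 |
| 24 months, +12 | 11.7 | 11.58 | 11.66 | 11.74 |
| 24 months, +12 | 14.3 | 14.03 | 14.23 | 14.49 |
| 24 months, +24 | either | no difference | no difference | no difference |

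The 11-month rows use the planned rate (22 patients / 2 per month, Section 16.3). The longest possible follow-up there is 11 + 6 = 17 months, so the medians sit in a thin tail. The upward shift in the last column arises because patients past PD, who are at higher risk, are censored earlier than patients still seen often.

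**With a closing check.** Censoring survivors at the cut gives the true median in every row. For 24 months, +6 and the 25% scenario, 18-month survival is 0.295 under the plan's rule and 0.332 with the check.

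**Against sampling error.** With 22 patients in that same case, mean 18-month survival is 0.299 against 0.336. The difference of 0.037 compares with a sampling SD of about 0.12.

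**The case against.** The strongest reply has four parts.

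1. **Not every survivor off treatment is on 6-monthly contact.** A reader might infer that from Section 4.2. Sections 4.1 and 13.3 rule it out: patients who stop without PD are seen every 9 weeks, to at most 18 months. This stands. The point is limited to patients in survival follow-up, and both runs put 25% on the 9-weekly schedule.

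2. **The documents do not say that late deaths are captured as they occur.** Section 10.52 requires 24-hour reporting only within 30 days of the last dose, or later if the death is at least possibly attributable to treatment. For other late deaths there is only the mark in the Section 4.2 table, without route or timing. This also stands, and it decides the sign. A flat statement that OS is biased downward is therefore not supported. It also means that under the current text the direction of error depends on unstated site practice, which argues for the status check.

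3. **The stop date is already common to all, and last follow-up may mean the date last known alive.** Nothing forbids a closing contact, and the timelines are called approximate. True, but nothing requires one either, and the date is not tied to the OS analysis.

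4. **It matters little.** OS is descriptive, the go/no-go rule in Section 16.4 uses PFS at 6 months only, and with 22 patients the KM median has a sampling SD of about 3-4 months. This stands as a limit on weight. It is no reason to keep an error that one check removes.

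**Conclusion.** The point holds in conditional form. Censoring at last follow-up, 6-monthly contact after PD, a separate death report and no closing check make ascertainment depend on vital status. To the extent that late deaths are reported promptly, OS is biased downward near the cut. With all deaths prompt, run 1 puts the median about 0.3-0.7 months low at 24-36-month accrual and a +6 cut.

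The figure of up to about 1.6 months should not be taken as the expected size. It needs 12-month accrual, and Section 1.4 points to slower recruitment: eligibility was widened at Amendment 4, when 11 patients with FGF19 expression had been enrolled. The +6 cut is not arbitrary, because Section 16.4 sets the final analysis around then and no separate OS analysis time is given. But follow-up may run longer, up to 31 Aug 2025, and at +18 months or later the bias in the median is about zero.

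The actual size is unknown because the documents give no registration dates. This is a cheap improvement to a secondary estimate and does not touch the primary decision.

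**What to change.** In Section 16.6.2:

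- Name one OS cut-off date, no later than 31 Aug 2025. A date slightly earlier would let the checks finish before monitoring stops.
- Confirm vital status at that date, by record review or a call, for every patient not known to have died.
- Censor confirmed survivors at the cut-off and count only deaths on or before it.
- If some patients' status cannot be confirmed, add a sensitivity analysis with an earlier common cut-off at which status is known for all, applied to deaths and survivors alike.

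The cost is a short addition to the SAP and one status check in at most 25 patients, the maximum accrual in Section 16.3.

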16.6.3 Incidence of Adverse Events (AEs)

Adverse events will be evaluated, per CTCAE v5.0, for each patient. Grade 3+ AEs, at least possibly related, which occur more than 10% of patients will be reported by grade.

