2.2 Secondary Goals

- 2.21 Assess the safety and tolerability of futibatinib and pembrolizumab combination through adverse event monitoring.
- 2.22 Determine the overall objective response rate (ORR) and overall survival (OS) of patients with advanced HCC treated with futibatinib and pembrolizumab combination.
- 2.23 Assess change in overall health-related quality of life, as measured by the global health domain of the European Organization for Research and Treatment of Cancer Quality of Life Questionnaire (EORTC-QLQ-C30) between baseline and at time of first-restaging scan.

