10.62 All other AEs

Submit via appropriate MCCC Case Report Forms (i.e., paper or electronic, as applicable) the following AEs experienced by a patient and not specified in Section 10.6:

10.621 Grade 2 AEs deemed *possibly, probably, or definitely* related to the study treatment or procedure.

10.622 Grade 3 and 4 AEs regardless of attribution to the study treatment or procedure.

10.623 Grade 5 AEs (Deaths)

10.6231 Any death within 30 days of the patient's last study treatment or procedure regardless of attribution to the study treatment or procedure.

10.6232 Any death more than 30 days after the patient's last study treatment or procedure that is felt to be at least possibly treatment related must also be submitted as a Grade 5 AE, with a CTCAE type and attribution assigned.

10.624 Outcome of Adverse Events

Record the outcome of AEs as follows:

- Resolved
- Not resolved/ Ongoing
- Fatal/ Death

10.625 Follow-up of Adverse Events

Any ongoing AEs should be followed until the earliest occurrence of one of the following:

- The AE has resolved or stabilized
- Completion of safety follow-up visit
- Start of new antitumor therapy
- Withdrawal of consent
- Death
- Other (eg, transfer to another hospital)

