15.25 Pharmacokinetic information

- a) Absorption – Because pembrolizumab is administered intravenously, it is immediately and completely bioavailable. Steady-state concentrations of pembrolizumab are reached by 16 weeks of repeated dosing with a Q3W regimen, and the systemic accumulation is 2.1-fold. The peak concentration, trough concentration, and area under the plasma concentration versus time curve at steady state of pembrolizumab increased dose proportionally in the dose range of 2 to 10 mg/kg Q3W.
- b) Distribution – Pembrolizumab has a limited volume of distribution.
- c) Excretion – CL is approximately 23% lower after achieving maximal change at steady state compared with the first dose. The terminal elimination half-life ($t_{1/2}$) is estimated to be 22 days at steady state.
- d) Metabolism - Pembrolizumab is catabolized through non-specific pathways; metabolism does not contribute to its CL.

15.26 **Potential Drug Interactions:** There are no known significant drug interactions.

15.27 Known potential adverse events:

Very common known potential adverse events, $\geq 10\%$:

Skin and subcutaneous tissue disorders: Pruritus, skin rash
Gastrointestinal disorders: Diarrhea, nausea, abdominal pain
General disorders and administration site conditions: fatigue

Common known potential adverse events, $>10\%$:

Blood and lymphatic system disorders: anemia
Immune system disorders: infusion related reaction
Endocrine disorders: hyperthyroidism, hypothyroidism
Metabolism and nutrition disorders: decreased appetite
Nervous system disorders: headache, dizziness, dysgeusia
Respiratory, thoracic, and mediastinal disorders: pneumonitis, dyspnea, cough
Gastrointestinal disorders: colitis, vomiting, constipation, dry mouth
Skin and subcutaneous tissue disorders: severe skin reactions, vitiligo, dry skin, erythema
Musculoskeletal and connective tissue disorders: arthralgia, myositis, musculoskeletal pain, arthritis, pain in extremity
General disorders and administration site conditions: asthenia, edema, pyrexia, influenza like illness, chills
Investigations: alanine aminotransferase increased, aspartate aminotransferase increased, blood alkaline phosphatase increased, blood creatinine increased

Uncommon known potential adverse events, 1% - 10%:

Infusion related reactions

Blood and lymphatic system disorders: neutropenia, thrombocytopenia, leukopenia, lymphopenia, eosinophilia

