Endocrine disorders: hypophysitis, adrenal insufficiency, thyroiditis, hypopituitarism
Metabolism and nutrition disorders: type I diabetes mellitus, hyponatremia, hypokalemia, hypocalcemia
Psychiatric disorders: insomnia, confusional state
Nervous system disorders: epilepsy, lethargy, peripheral neuropathy
Eye disorders: uveitis, dry eye
Cardiac disorders: myocarditis, atrial fibrillation
Vascular disorders: hypertension
Gastrointestinal disorders: pancreatitis
Hepatobiliary disorders: hepatitis
Skin and subcutaneous tissue disorders: lichenoid keratosis, psoriasis, alopecia, dermatitis, dermatitis acneiform, eczema, hair color changes, papule
Musculoskeletal and connective tissue disorders: tenosynovitis
Renal and urinary disorders: nephritis, acute kidney injury
Investigations: blood bilirubin increased, amylase increased, hypercalcemia

Rare known potential adverse events, $<1\%$ (Limited to important or life-threatening):

Blood and lymphatic system disorders: immune thrombocytopenic purpura, hemolytic anemia
Immune system disorders: sarcoidosis
Nervous system disorders: Guillain-Barre syndrome, myasthenic syndrome
Gastrointestinal disorders: small intestinal perforation

Skin and subcutaneous tissue disorders: toxic epidermal necrolysis, Stevens-Johnson syndrome, erythema nodosum

The risk profile for pembrolizumab also includes two important potential risks: a) myasthenic syndrome, and b) an increased risk of severe complications (such as early severe graft versus host disease and veno-occlusive disease) of allogeneic transplant in patients with hematologic malignancies who have previously been treated with PD-1 inhibitors.

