16.72 Adverse Event Stopping Rules

The stopping rules specified below are based on the knowledge available at study development. We note that the Adverse Event Stopping Rule may be adjusted in the event of either (1) the study re-opening to accrual or (2) at any time during the conduct of the trial and in consideration of newly acquired information regarding the adverse event profile of the treatment(s) under investigation. The study team may choose to suspend accrual because of unexpected adverse event profiles that have not crossed the specified rule below.

Accrual will be temporarily suspended to this study if at any time, we observe events considered to be at least possibly related to study treatment (i.e., an adverse event with attribute specified as “possible”, “probable”, or “definite”) that satisfy the following:

- If at any time, 4 of the initial 10 treated patients or 40% or more of all patients (i.e., when accrual is greater than 10 patients) have experienced a Grade 4+ adverse event at least possibly related to study treatment. per NCI Common Terminology Criteria for Adverse Events v.5.0, excluding the following:
 - Grade 4 white blood cell decreased lasting ≤ 3 days
 - Grade 4 platelet count decreased lasting ≤ 3 days
 - Grade 4 electrolyte alteration* lasting ≤ 3 days

*Electrolyte alterations include the following events in SOC
“Metabolism and nutrition disorders”

- Hyperglycemia or Hypoglycemia
- Hyperkalemia or Hypokalemia

We note that we will review Grade 4 and 5 adverse events deemed “unrelated” or “unlikely to be related”, to monitor the emergence of a previously unrecognized treatment-related adverse event.

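### The planned adverse event result is split by FGF19 status and limited to related Grade 3+ events in more than 10% of patients, so a severe event type seen in 1 or 2 of 22 patients is left out

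*Combined protocol and SAP*

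**What the plan says.** Section 16.6 sets the population for all secondary analyses, adverse events included: "The below analyses will be done on FGF19 positive patients". It adds: "The analyses will also be performed on FGF19 negative patients as exploratory analyses". No pooled analysis is mentioned.

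Section 16.6.3 has two sentences. The first says that events are evaluated for each patient under CTCAE v5.0 and defines no summary. The second is the only reporting rule: "Grade 3+ AEs, at least possibly related, which occur more than 10% of patients will be reported by grade". It names no denominator, does not say whether the cut applies to each event term, and makes no exception for Grade 5.

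Other parts of the protocol are not limited by FGF19 status. The first secondary goal (2.21) is: "Assess the safety and tolerability of futibatinib and pembrolizumab combination through adverse event monitoring". The stopping rule in 16.72 counts "4 of the initial 10 treated patients or 40% or more of all patients". Section 10.62 collects "Grade 3 and 4 AEs regardless of attribution to the study treatment or procedure", together with deaths within 30 days of the last study treatment or procedure and later deaths at least possibly related to treatment.

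**The concern.** Two features of the plan restrict what the final safety result will show.

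- **The frequency cut.** In a group of about 22, a cut at more than 10% removes every event type seen in 1 or 2 patients, whatever its grade. Section 1.2 says there are no clinical data on futibatinib with immunotherapy in HCC, so uncommon severe events are part of what this trial should describe. Section 15.27 places hepatitis, myocarditis, adrenal insufficiency and nephritis in its 1% to 10% band for pembrolizumab, at or below the cut.
- **The split by FGF19 status.** The regimen and the safety question are the same for all treated patients. Since Amendment 4, patients enter regardless of FGF19 expression and are tested retrospectively (Section 1.4). The final safety result is therefore divided by a marker that may be unknown at dosing. A treated patient whose test gave no result would belong to neither group.

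At stake is a reported safety profile that omits a related severe, or even fatal, event type that did occur.

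**Working it through.** **Inputs.** Evaluable target 22 and maximum accrual 25 (16.3); cut at more than 10% (16.6.3); 5 of 36 screened patients without FGF19 expression and 11 patients with expression already enrolled (1.4). The true event rates below are assumptions. The protocol gives no rates for related Grade 3+ events on the combination.

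**Step 1: the floor.** Find the smallest k with k/n > 0.10.

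- n = 22: 2/22 = 9.1% fails; 3/22 = 13.6% passes.
- n = 25: 2/25 = 8.0% fails; 3/25 = 12.0% passes.
- The floor is 3 patients for n = 20 to 29, 2 patients for n = 10 to 19, and 1 patient for n = 1 to 9.

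The rule therefore acts differently in the two groups. One case among fewer than 10 FGF19-negative patients is reported, while two cases among 22 FGF19-positive patients are not.

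**Step 2: chance that an event type occurs but is not reported.** With X binomial(n, p), this is P(1 ≤ X ≤ 2) = P(X ≤ 2) − P(X = 0). For n = 22 and p = 0.05, it is 0.905 − 0.324 = 0.582.

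| Assumed true rate | n = 22 | n = 25 | Share below the cut, given at least one case, n = 22 |
|---|---|---|---|
| 1% | 0.20 | 0.22 | 0.99 |
| 2% | 0.35 | 0.38 | 0.97 |
| 5% | 0.58 | 0.60 | 0.86 |
| 10% | 0.52 | 0.47 | 0.58 |
| 15% | 0.31 | 0.24 | 0.32 |

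The last column is P(1 ≤ X ≤ 2) / [1 − P(X = 0)]; at 5% it is 0.582/(1 − 0.324) = 0.86.

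An event seen in 2 of 22 patients has an exact 95% interval of 1.1% to 29.2%, so falling below the cut does not show that an event is rare.

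**Step 3: size of the FGF19-negative group.** If the screening fraction applies to the remaining places, (25 − 11) × 5/36 = 1.9 patients. The exact 95% interval for 5/36 is 4.7% to 29.5%, which gives 0.7 to 4.1 patients.

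**Step 4: effect of the split alone.** An event in 2 of 22 positive patients (9.1%) and 1 of 2 negative patients is 3 of 24 pooled (12.5%): above the cut when pooled, absent from the main result. This is uncommon. With 22 positive and 2 negative patients, the chance that the positive group has at most 2 cases and the pooled group at least 3 is 0.3%, 2.1%, 5.6% and 5.8% at true rates of 2%, 5%, 10% and 15%. Pooling without removing the cut would still require 3 of 25 patients.

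**The case against.** The strongest reply is that no trial decision rests on 16.6.3. Efficacy is judged on PFS6, and safety is guarded by the run-in (7.5), the Grade 4+ stopping rule over all patients (16.72) and DSMB review (16.71). Severe events are collected regardless of attribution, and deaths count in overall survival. All of this is true, and it limits the point to the reported result. It does not answer the point, because none of those provisions defines what will be reported for goal 2.21.

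A second reply is that the rule is a minimum: Section 16.2 names incidence of adverse events without a threshold, and nothing says other events will be withheld. That is a possible reading, and the per-term reading used here is also not explicit. Still, the plan commits to nothing beyond the stated rule.

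Third, the split has little numerical effect. This stands: Step 4 puts it at about 0.3% to 6%, and in the example the negative patient's event (1 of 2) would pass the rule in the exploratory analysis.

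Fourth, the list in 15.27 is for pembrolizumab alone, without grade or attribution. This also stands, so it cannot supply a rate for the combination. For pembrolizumab itself, however, related Grade 3+ rates cannot exceed the listed any-grade rates, so the cut is still at or above them.

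Finally, if fewer than 20 FGF19-positive patients are analysed, the floor falls to 2. An event type seen in one patient is then still omitted for any n of 10 or more.

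**Conclusion.** The concern holds. Followed as written, 16.6.3 leaves out of the safety result any related Grade 3 to 5 event type seen in 1 or 2 of 22 FGF19-positive patients. The floor of 3 patients is arithmetic for any n from 20 to 29, given the per-term reading. For true rates of 2% to 15%, the chance that an event type occurs and goes unreported is 0.31 to 0.58 at n = 22; at 1% it is 0.20. These probabilities depend on the assumed rates, but the floor does not. The FGF19 split is a secondary defect: it fits neither goal 2.21 nor the all-patient basis of 16.72, but its numerical effect is small if only about 2 FGF19-negative patients enter. Collection and monitoring of events are not in question. The plan should be changed, and the change is cheap.

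**What to change.** In 16.6, exempt adverse events from the FGF19 restriction and define the main safety population as all patients who received any dose of either drug, regardless of FGF19 status or test result. Show FGF19 subgroups as supportive only.

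In 16.6.3, tabulate all related Grade 3+ events by term and maximum grade, with no frequency filter and with the denominator stated, and list every Grade 5 event. A parallel table regardless of attribution is optional. Both changes are needed, since pooling alone still requires 3 of 25 patients. Without the filter, the floor at n = 22 falls from 3 patients (13.6%) to 1 (1/22 = 4.5%).

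The cost is wording in two sections and a longer table. Section 10.62 already collects the data, so no visits, samples or patients are added.
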